10.5 Safety Analyses

All safety analyses will be carried out separately for each of the groups (CORI Robotics UKA and CORI Robotics TKA groups) and overall as follows:

- The number of adverse events will be reported both overall and by seriousness, relationship to study device and anticipation.
- The number of subjects experiencing adverse events will be summarised both overall and by seriousness, relationship to study device and anticipation.
- An overall AE summary table that will summarize as number (n) and percentages (%), the overall incidence according to subjects with at least one AE; subjects with at least one AE by worst severity (mild, moderate, or severe); subjects with at least one AE by worst outcome (resolved, ongoing/unresolved, or death); subjects with an AE that led to study discontinuation) and; subjects with at least one AE by worse relatedness to device. Other events such as SAEs, ADEs, SADEs or UADEs will also be similarly summarized using the number (n) and percentages (%).
- Incidence of device-related re-interventions that occur on-study will be summarized as number (n) and percentages as well as by type.
- A listing of device deficiencies that occur on-study will be provided.
- Knee implant revision rate will be summarized as proportions with 95% CIs estimated using exact binomial methods.

All safety endpoints will be summarized using the SAF analysis population.

10.6 Interim Analyses

Not applicable.

11. SAMPLE SIZE JUSTIFICATION

Parratte et al.[53] looked at the effects of postoperative mechanical axis alignment on the survival of TKAs. They found that of the 398 TKAs reviewed in the paper there were 292 (73.4%) which post-operatively were defined as mechanically aligned (i.e. with a mechanical axis of $0^\circ \pm 3^\circ$).

This study is designed to demonstrate superiority in the proportion of TKAs post-operatively defined as mechanically aligned against the reference proportion of 73.4% from above.

Clinical Protocol

A Prospective, Multi-center, Study to Evaluate the Safety and Effectiveness of REAL INTELLIGENCE™ CORI™ in unicondylar knee arthroplasty (UKA) and total knee arthroplasty (TKA) procedures

Study Number: CORI.2019.07

Version: 6.0, 15/Jan/2024

Page: 60 of 122

The proportion of mechanically aligned TKAs using the NAVIO™ Surgical System from a recent analysis was estimated to be 92.1% [54]. If this assumption holds for this study, then the enrollment of 36 knees for each of the two planned study groups (i.e. the CORI Robotics UKA and CORI Robotics TKA) for a total of 72 knees will individually provide approximately 80% power to show that the lower limit of the two-sided 95% confidence interval for the proportion of mechanically aligned TKAs is greater than that obtained from literature. To account for up to a 10% attrition rate in knees enrolled, 40 knees in each group (80 knees combined, 40 UKA, 40 TKA) will be enrolled in the study.

12. ADVERSE EVENTS AND DEVICE DEFICIENCIES

12.1 Definitions

The categories of adverse events are shown in table 12.1-1. The definitions for each of these categories are given in the subsequent sections.

Table 12.1-1: Categories of Adverse Event

	NOT DEVICE-RELATED	DEVICE- OR PROCEDURE- RELATED	
Non-Serious	Adverse Event (AE)	Adverse Device Effect (ADE)	
Serious	Serious Adverse Event (SAE)	Serious Adverse Device Effect (SADE) (See 12.1.3)	
		Anticipated	Unanticipated
		Anticipated Serious Adverse Device Effect (ASADE)	Unanticipated Serious Adverse Device Effect (USADE)

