- Posterior stabilized knee systems are designed for use in patients in primary and revision surgery, where the anterior and posterior cruciate ligaments are incompetent and the collateral ligaments remain intact.

For this study only the CORI Robotics is considered the IP and not the implant systems used.

All surgeons using CORI Robotics will have previously been fully trained on the use of the system by S+N staff.

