12.1.2 Adverse Device Effect

An Adverse Device Effect (ADE) is an adverse event related to the use of an investigational medical device.

Note 1: This definition includes adverse events resulting from insufficient or inadequate instructions for use, deployment, implantation, installation or operation, or any malfunction of the investigational medical device.

Note 2: This definition includes any event resulting from use error or from intentional misuse of the investigational medical device.

Note 3: This includes "comparator" if the comparator is a medical device.

Not Related - An AE is considered to be not related to the use of an IP or the procedure when the effect is DEFINITELY UNRELATED to have any relationship to the use of the IP or the procedure.

Related – An AE is considered to be related to the use of an IP or the procedure when there is a POSSIBLE, or DEFINITE relationship between the AE and the use of the IP or the procedure.

An ADE is further categorized depending on whether the criteria in section 12.1.3 and 12.1.4 are met.

Clinical Protocol

A Prospective, Multi-center, Study to Evaluate the Safety and Effectiveness of REAL INTELLIGENCE™ CORI™ in unicondylar knee arthroplasty (UKA) and total knee arthroplasty (TKA) procedures

Study Number: CORI.2019.07

Version: 6.0, 15/Jan/2024

Page: 62 of 122

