12.1.4 Anticipated/Unanticipated Serious Adverse Device Effect

An Unanticipated Serious Adverse Device Effect (USADE) is a serious ADE which by its nature, incidence, severity or outcome has not been identified in the current version of the risk assessment.

Note 1: Anticipated serious adverse device effect (ASADE) is an effect which by its nature, incidence, severity, or outcome has been identified in the risk assessment. A list of potential ASADE for the CORI Robotics is provided in but not limited to Table 12.1-2. Please also refer to Section 4.4.6 Anticipated Risks / Adverse Effects and the current IFUs (Appendix 22.2).

Clinical Protocol

A Prospective, Multi-center, Study to Evaluate the Safety and Effectiveness of REAL INTELLIGENCE™ CORI™ in unicondylar knee arthroplasty (UKA) and total knee arthroplasty (TKA) procedures

Study Number: CORI.2019.07

Version: 6.0, 15/Jan/2024

Page: 63 of 122

Table 12.1-2 Potential Anticipated Serious Adverse Device Effects (ASADE)

#	Potential Harm	Description
1	Allergic Reaction to Materials	Hypersensitivity caused by exposure to material constituents of the product that leads to local inflammatory reaction and tissue damage. Contact with an allergen may cause swelling and redness of the skin in minor cases. A severe anaphylactic reaction may occur.
2	Bone Fracture	Any break or fracture to any bone. (Applicable to displaced and non-displaced fractures) The bone break could be reduced (set) and immobilized during the same surgery during which it occurred if it is detected. If the fracture occurs after the surgery, additional medical attention would be required. Subsequent healing returns normal body function for the subject.
3	Burn	3 rd degree burn extending through the dermis which requires excision. 4 th degree burn extending into the subcutaneous tissue, muscle and bone with eschar formation. Burns may be caused by thermal or chemical burns.
4	Cardiac Arrhythmia - symptomatic	Variation from the normal heart rhythm symptomatic.
5	Cement Leakage	Cement can end up in an unintended location in the joint. Cement leakage may cause early wear of poly or pain to the subject and may require revision surgery.

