12.3 Reporting procedures

AE of any kind and DD will be recorded in the applicable CRF and source notes to include the date of occurrence, treatment, and the details resolution. The Investigator will evaluate all AE for relationship to the device and procedure, seriousness, and severity (if applicable). DD will be evaluated for potential to cause SADE. The following timescales should be followed for the AE/DD information to be submitted/entered into the CRF and reported to the Sponsor or designee (see figure 12.2-1):

- ADE and DD – without unreasonable delay
- SAE, SADE, and DD with potential to cause SADE – immediately (i.e. within 24 hours of the investigator being informed about the event)
- All other events – according to usual timescales

In addition to inputting SAE and SADE information within 24 hours of being aware of the event, the investigator should email [contact] to alert the safety representative of the events existence and to clarify details if necessary.

For ADE and DD, date of occurrence, and details of the product/procedure related to the event will be included and where applicable, pictures taken of the device. The deficient product should be retained for return to S+N unless it is contaminated (e.g., used dressings must not be retained). Updates to submitted information will be recorded in the CRF according to the timescales above.

All adverse events will be reviewed by a medically qualified person appointed by the Sponsor to determine which, if any, meet criteria for expedited reporting to the regulatory authorities.

The investigator will inform the regulatory agency and IRB/IEC of adverse events as per the requirements listed below:

Unanticipated SADE's and DD's that could have led to SADE will be reported to IEC/IRB and regulatory authorities within 10 working days.

Clinical Protocol

A Prospective, Multi-center, Study to Evaluate the Safety and Effectiveness of REAL INTELLIGENCE™ CORI™ in unicondylar knee arthroplasty (UKA) and total knee arthroplasty (TKA) procedures

Study Number: CORI.2019.07

[figure not shown]
Version: 6.0, 15/Jan/2024

Page: 67 of 122

All other events will be reported on a periodic/annual basis.

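### The protocol gives two incompatible definitions of an adverse device effect, so a complication of the surgery alone can be counted as either AE/SAE or ADE/SADE

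*Combined protocol and SAP*

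**What the plan says.** Section 12.1 opens with Table 12.1-1, which has two relatedness columns. The first, "NOT DEVICE-RELATED", holds AE and SAE. The second, "DEVICE- OR PROCEDURE- RELATED", holds ADE and SADE, with SADE divided into ASADE and USADE.

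Section 12.1.2 defines the central term by the device alone: "An Adverse Device Effect (ADE) is an adverse event related to the use of an investigational medical device". Section 6.1.1 fixes what the device is: "For this study only the CORI Robotics is considered the IP and not the implant systems used". Yet the relatedness rule further down Section 12.1.2 joins the two causes: "An AE is considered to be related to the use of an IP or the procedure when there is a POSSIBLE, or DEFINITE relationship".

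The downstream terms inherit whichever ADE definition is used. Section 12.1.3 makes a serious ADE a SADE. Section 12.1.4 says "An Unanticipated Serious Adverse Device Effect (USADE) is a serious ADE which by its nature, incidence, severity or outcome has not been identified". Section 12.3 attaches a deadline: "Unanticipated SADE's and DD's that could have led to SADE will be reported to IEC/IRB and regulatory authorities within 10 working days". All other events go to those bodies periodically or annually.

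Section 10.5 plans counts of events and of subjects "by seriousness, relationship to study device and anticipation". It also plans numbers and percentages for SAEs, ADEs, SADEs and UADEs. It mentions no breakdown by relationship to the procedure.

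**The concern.** The study is meant to show the safety of the robot, and the robot alone is the investigational product. Knee arthroplasty has complications of its own, some of which will have nothing to do with CORI. Whether such a complication counts as a device effect should be settled by one rule. Here, the ADE sentence in Section 12.1.2 excludes it, the second column of Table 12.1-1 includes it, and the relatedness rule in Section 12.1.2 sides with the table.

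At stake is the meaning of the ADE, SADE and UADE rows in the safety tables and, for a narrow class of events, the route by which an ethics committee or authority hears of them.

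**Working it through.** There is no stated figure to reproduce. The check compares the definitions and follows one event through each of them.

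**1. Do the table's columns partition events?** Let D mean related to the device and P related to the procedure. The first column is *not D*; the second is *D or P*. Together they cover every event, but they overlap where *not D and P* holds.

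| Relatedness | ADE sentence, 12.1.2 | Table 12.1-1 | Relatedness rule, 12.1.2 |
|---|---|---|---|
| Device only | ADE/SADE | ADE/SADE | Related |
| Device and procedure | ADE/SADE | ADE/SADE | Related |
| Procedure only | AE/SAE | fits both columns | Related |
| Neither | AE/SAE | AE/SAE | Not related |

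Only the procedure-only row is unsettled. Note 1 to the ADE definition widens it to inadequate implantation, installation or operation, but this still concerns the investigational device and so does not reach procedure-only events.

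**2. What changes for a procedure-only event?** The timelines are from Section 12.3.

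| Event | Device-only reading | Device-or-procedure reading | What differs |
|---|---|---|---|
| Non-serious | AE, usual timescales | ADE, without unreasonable delay | Count and site-to-sponsor timing |
| Serious, in the risk assessment | SAE, 24 hours to sponsor, then periodic/annual | ASADE, the same timings | Count only |
| Serious, not in the risk assessment | SAE, 24 hours to sponsor, then periodic/annual | USADE, 24 hours to sponsor, then 10 working days to IEC/IRB and authorities | Count and external reporting |

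**3. What does this do to Section 10.5?** Under the device-only reading, events labelled ADE or SADE are the device-related events. Under the other reading, they are the device-related events plus the procedure-only events. The ADE/SADE counts and the device-relationship counts in one report then differ by exactly the number of procedure-only events, with no planned row to explain the gap.

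**4. Can the size be given?** Only per subject. With 40 subjects planned per group, each further subject who enters a row solely through a procedure-only event moves it by 1/40 = 2.5 percentage points, or 1/80 = 1.25 points overall. The documents give no expected number of such subjects, so no total follows.

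**5. Terminology.** Section 10.5 uses UADE where Section 12 uses USADE, so the row meant to hold unanticipated serious effects is not tied by name to its definition.

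**The case against.** The strongest case on the other side has four parts.

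*The table is only an overview.* Section 12.1 says the definitions follow in later sections, so the text could be taken to govern. That does not settle it, because Section 12.1.2 contains both the device-only sentence and the merged relatedness rule. For the same reason, a reader who sees a plain conflict of text against table has it slightly wrong: one section supports both readings.

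*The device rate is not lost.* A reader might infer that the plan cannot deliver a clean CORI-related rate. The documents do not support that. Section 12.3 has the investigator judge relationship to the device and to the procedure, Section 8.3.4 names both, and Section 10.5 tabulates by relationship to the device. If device causality is recorded separately, the device-related rate can be recovered whichever ADE definition is used. This part stands. The protocol does not, however, expressly require two separate fields, and the relatedness rule invites a single combined answer.

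*Expedited reporting is mostly untouched.* A reader might infer that expedited reporting in general depends on which section a site follows. It does not. SAEs and SADEs share the 24-hour rule, a medically qualified person appointed by the sponsor reviews all AEs, and Table 12.1-2 lists 15 anticipated harms, including infection, fracture and nerve and vascular injury, without claiming to be exhaustive. Many serious surgical complications would therefore be ASADEs at most, with the same timings as SAEs. This also stands. Central review may reduce differences between sites, but the reviewer is given the same unreconciled definitions, and the stated remit is expedited reporting, not relabelling for Section 10.5.

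*The stakes are modest.* Safety is summarised descriptively, without a comparator or an AE hypothesis, and the primary endpoint is not involved. That is correct and limits the weight of the point.

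It is also tempting to illustrate with assumed complication counts and conclude that ADE incidence rises several-fold. Nothing in the documents supplies those counts, so such a contrast would reflect only the assumption.

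**Conclusion.** The point holds as an internal contradiction in the current protocol text. A procedure-only event has two defensible labels, so the ADE, SADE and UADE counts in Section 10.5 have no single meaning and may not agree with the device-relationship counts beside them. The reporting consequence is confined to the timing of non-serious events and to serious, procedure-only, unanticipated events. The size of the shift in counts cannot be stated. It is zero if no procedure-only events occur, and otherwise the broader reading gives the higher ADE/SADE event counts.

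Two limits apply. The AE evaluation flowchart in Section 12.3 was not visible in the text reviewed and may contain a decision rule. Section 10 also describes itself as a brief account of a fuller SAP, where table layout may be settled. Neither would remove the conflict between Table 12.1-1 and Section 12.1.2. The matter should be corrected, but it does not threaten the primary analysis.

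**What to change.** - Reconcile Table 12.1-1 with Section 12.1.2, including its relatedness rule, so that there is one ADE definition. Which definition to adopt is for the sponsor to decide; the sections must agree.
- Reword the table's column headings so that they are mutually exclusive and a procedure-only event falls in exactly one.
- State in Section 12.3 that relatedness to CORI and relatedness to the procedure are recorded as two separate fields.
- In Section 10.5, tabulate AEs and SAEs as CORI-related, procedure-related only, or neither.
- Use one term, USADE or UADE, throughout.

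The cost is a wording amendment, with the approvals Section 16 requires, and one extra row split in the safety tables. The causality judgements are already required by Section 12.3. If the eCRF holds only a combined relatedness answer, a field must be added and events already entered must be queried.

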12.1.1 Adverse Event

An Adverse Event (AE) is any untoward medical occurrence, unintended disease or injury or untoward clinical signs (including abnormal laboratory findings) in subjects, users or other persons, whether or not related to the investigational medical device and whether anticipated or unanticipated.

Note 1: This definition includes events related to the investigational medical device or the comparator.

Clinical Protocol

A Prospective, Multi-center, Study to Evaluate the Safety and Effectiveness of REAL INTELLIGENCE™ CORI™ in unicondylar knee arthroplasty (UKA) and total knee arthroplasty (TKA) procedures

Study Number: CORI.2019.07

Version: 6.0, 15/Jan/2024

Page: 61 of 122

Note 2: This definition includes events related to the procedures involved.

Note 3: For users or other persons, this definition is restricted to events related to the use of investigational medical devices or comparators.

AE is used both to refer to AE which do not meet the definitions of Adverse Device Effects or Serious Adverse Events and as an umbrella term referring to adverse events of all classifications.

An AE can be any unfavorable and unintended sign (for example, an abnormal laboratory finding), symptom, or disease. For reporting purposes, emphasis is placed first and foremost on whether or not the event constitutes an untoward medical occurrence.

12.1.2 Adverse Device Effect

An Adverse Device Effect (ADE) is an adverse event related to the use of an investigational medical device.

Note 1: This definition includes adverse events resulting from insufficient or inadequate instructions for use, deployment, implantation, installation or operation, or any malfunction of the investigational medical device.

Note 2: This definition includes any event resulting from use error or from intentional misuse of the investigational medical device.

Note 3: This includes "comparator" if the comparator is a medical device.

Not Related - An AE is considered to be not related to the use of an IP or the procedure when the effect is DEFINITELY UNRELATED to have any relationship to the use of the IP or the procedure.

Related – An AE is considered to be related to the use of an IP or the procedure when there is a POSSIBLE, or DEFINITE relationship between the AE and the use of the IP or the procedure.

An ADE is further categorized depending on whether the criteria in section 12.1.3 and 12.1.4 are met.

Clinical Protocol

A Prospective, Multi-center, Study to Evaluate the Safety and Effectiveness of REAL INTELLIGENCE™ CORI™ in unicondylar knee arthroplasty (UKA) and total knee arthroplasty (TKA) procedures

Study Number: CORI.2019.07

Version: 6.0, 15/Jan/2024

Page: 62 of 122

12.1.3 Serious Adverse Events and Serious Adverse Device Effects

An AE or ADE is considered a **Serious** Adverse Event (SAE) or **Serious** Adverse Device Effects (SADE) if, it led to any of the following:

- a) death,
- b) serious deterioration in the health of the subject, users or other persons as defined by one or more of the following:
 - 1) a life-threatening illness or injury, or
 - 2) a permanent impairment of a body structure or a body function including chronic diseases, or
 - 3) in-patient or prolonged hospitalization, or
 - 4) medical or surgical intervention to prevent life-threatening illness or injury or permanent impairment to a body structure or a body function,
- c) foetal distress, foetal death or a congenital abnormality or birth defect including physical or mental impairment

Note 1: Planned hospitalization for a pre-existing condition, or a procedure required by the study protocol, without serious deterioration in health, is not considered a serious adverse event.

12.1.4 Anticipated/Unanticipated Serious Adverse Device Effect

An Unanticipated Serious Adverse Device Effect (USADE) is a serious ADE which by its nature, incidence, severity or outcome has not been identified in the current version of the risk assessment.

Note 1: Anticipated serious adverse device effect (ASADE) is an effect which by its nature, incidence, severity, or outcome has been identified in the risk assessment. A list of potential ASADE for the CORI Robotics is provided in but not limited to Table 12.1-2. Please also refer to Section 4.4.6 Anticipated Risks / Adverse Effects and the current IFUs (Appendix 22.2).

Clinical Protocol

A Prospective, Multi-center, Study to Evaluate the Safety and Effectiveness of REAL INTELLIGENCE™ CORI™ in unicondylar knee arthroplasty (UKA) and total knee arthroplasty (TKA) procedures

Study Number: CORI.2019.07

Version: 6.0, 15/Jan/2024

Page: 63 of 122

Table 12.1-2 Potential Anticipated Serious Adverse Device Effects (ASADE)

#	Potential Harm	Description
1	Allergic Reaction to Materials	Hypersensitivity caused by exposure to material constituents of the product that leads to local inflammatory reaction and tissue damage. Contact with an allergen may cause swelling and redness of the skin in minor cases. A severe anaphylactic reaction may occur.
2	Bone Fracture	Any break or fracture to any bone. (Applicable to displaced and non-displaced fractures) The bone break could be reduced (set) and immobilized during the same surgery during which it occurred if it is detected. If the fracture occurs after the surgery, additional medical attention would be required. Subsequent healing returns normal body function for the subject.
3	Burn	3 rd degree burn extending through the dermis which requires excision. 4 th degree burn extending into the subcutaneous tissue, muscle and bone with eschar formation. Burns may be caused by thermal or chemical burns.
4	Cardiac Arrhythmia - symptomatic	Variation from the normal heart rhythm symptomatic.
5	Cement Leakage	Cement can end up in an unintended location in the joint. Cement leakage may cause early wear of poly or pain to the subject and may require revision surgery.
6	Unstable knee joint	The implant components are placed in such a way that there is too much laxity in the ligaments. The subject experiences instability throughout the range of motion, There is an increased risk of early loosening/ wear of the implant. This may impact the stability and wear of implant components. Implants loosening could lead to early revision surgery.
7	Restricted Range of Motion	The implants are placed in such a way that excessive forces are placed on the ligaments (ACL, PCL, MCL, and LCL). This leads to an unintended reduction in the range of motion or progression of disease in a non- operative compartment. This may be serious, if the subject's range of motion has been worsened compared to the range of motion prior to surgery, or it has been restored sub-optimally.

Clinical Protocol

A Prospective, Multi-center, Study to Evaluate the Safety and Effectiveness of REAL INTELLIGENCE™ CORI™ in unicondylar knee arthroplasty (UKA) and total knee arthroplasty (TKA) procedures

Study Number: CORI.2019.07

Version: 6.0, 15/Jan/2024

Page: 64 of 122

#	Potential Harm	Description
8	Infection	
Invasion and multiplication of microorganisms in body tissues, especially microorganisms causing local cellular injury due to competitive metabolism, toxins, intracellular replication, or antigen-antibody response. The infection may lead to a diseased state in the receiving host if the host has inadequate resistance and/or lacks immunity to overcome the invasion by the pathogen.
 
Most typically, the resultant disease state can be treated through the use of antibiotics. When the pathogen is particularly virulent, or when the host has low resistance, the disease state may lead to a permanent impairment of some aspect of bodily function or, in extreme cases, to death. Infections caused by a transfer of body fluids during orthopedic surgery can in most cases be treated by a course of antibiotics. Severe infections that can occur by the transfer of body fluids during the procedure include HIV and hepatitis.

9	Delay	A delay in the operation time exceeding 60 minutes of intra-operative case time. A wound being open longer would more likely result in soft tissue edema, increased blood loss, muscle necrosis as a result of extended tourniquet time and a higher chance of infection.
10	Immature implant failure	Implant components wear before their intended service life resulting in early revision surgery.
11	Neurological Injury	Damage to the nerve systems of the subject's leg. A neurological injury could result in temporary or permanent paralysis.
12	Physical Injury - Serious	A physical injury that necessitates medical intervention.
13	Soft Tissue Damage	Damage to ligaments or tendons leading to loss of stability in the knee joint. In severe cases of ligament damage, additional surgery may be required.
14	Surgeon Operates on Wrong Part of Anatomy	The clinical impacts of operating on the wrong subject anatomy relate to the resultant function of the skeletal element that was treated and the need to repeat treatment for the desired skeletal element. The impact on the subject may be additional surgery under full anesthesia.

Clinical Protocol

A Prospective, Multi-center, Study to Evaluate the Safety and Effectiveness of REAL INTELLIGENCE™ CORI™ in unicondylar knee arthroplasty (UKA) and total knee arthroplasty (TKA) procedures

Study Number: CORI.2019.07

Version: 6.0, 15/Jan/2024

Page: 65 of 122

#	Potential Harm	Description
15	Vascular Injury - Main Low-extremity vessels	Damage to the vascular systems of the subject's leg. In severe cases, dis-vascularization occurs that is, the subject loses blood flow to the leg when a clot forms in significant arteries of the leg. Additional surgery would be required to correct blood flow. If blood flow to the leg is not restored, the patient's leg may need to be amputated.

